7.1.2. Safety Analysis Population

The safety analysis population will consist of all enrolled subjects who received at least one injection of flortaucipir under the AV-1451-A18 protocol.

7.1.3. Efficacy Analysis Population

This population includes all subjects in safety population for whom valid image data are available for the AV-45-A18 flortaucipir scan. All primary analyses will be based on this population.

8. DISPOSITION AND WITHDRAWALS

The entire screened population will be represented in the disposition table. The disposition table be broken down by diagnosis groups and include a summary of:

- Total number of enrolled subjects
- Total number of subjects in the safety population
- Number of subjects in the efficacy population
- Number of Completed Subjects
- Number of Discontinued Subjects

The disposition table will also include details on discontinuation reasons:

- Protocol Violation
- Adverse Event
- Physician Decision
- Pregnancy
- Study Terminated by Sponsor
- Lost to Follow-up
- Technical Problems
- Withdrawal by Subject
- Death
- Other

Termination Status (i.e. 'Completed' and 'Discontinued') percentages will be based on the safety population. Percentages outlining discontinuation reasons will be based on the number of discontinued subjects.

Subject disposition will be presented in a listing with the following information.

- Date of Consent
- Date Subject Ended Study
- Did Subject Complete Study? (Yes/No); Reason for Discontinuation, if No

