3.3. Randomization and Blinding

This is an open label, non-randomized study. All subjects who qualify for the study and sign informed consent will receive a single IV bolus of flortaucipir.

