4.3.1. Safety Follow-up/Phone Call

Each study subject (or caregiver/informant if applicable) will be contacted 2 or 3 business days after flortaucipir administration, but not prior to 48 hours post-injection, to collect any new adverse events. End of study for the purpose of adverse event reporting and study participation is defined as 48 hours after flortaucipir administration.

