7. ANALYSIS POPULATIONS

7.1.1. Enrolled Population

Subjects who participated in the 18F-AV-1451-A05 confirmatory cohort, meet the inclusion/exclusion criteria of 18F-AV-1451-A18, have consented to be enrolled in this study, and have baseline data captured in the AV-1451-A05 eCRF database will consist of the enrolled population.

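### Completed and Discontinued percentages use injected subjects as the denominator, so they sum to more than 100% if any enrolled subject leaves before the injection

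*SAP*

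**What the plan says.** SAP section 8 sets the scope of the disposition table broadly: "The entire screened population will be represented in the disposition table". Broken down by diagnosis group, the table gives the numbers enrolled, in the safety population, in the efficacy population, completed and discontinued. For completed and discontinued, the section states that the "percentages will be based on the safety population". Reasons have their own base: "Percentages outlining discontinuation reasons will be based on the number of discontinued subjects".

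The two populations differ by the injection:

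- **Safety (SAP 7.1.2):** "all enrolled subjects who received at least one injection of flortaucipir under the AV-1451-A18 protocol".
- **Enrolled (SAP 7.1.1):** confirmatory-cohort subjects of the A05 study who meet the eligibility criteria, "have consented to be enrolled in this study, and have baseline data captured in the AV-1451-A05 eCRF database will consist of the enrolled population". No injection is needed.

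Protocol 8.3, under Discontinuation, asks for a listing of every subject who stops before completing the study and a tabulation of the reasons. It does not confine this to injected subjects.

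**The concern.** A subject who consents, is enrolled and then leaves before the PET visit belongs in the table and, on the plain reading, in the discontinued count. That subject is not in the denominator, so the numerator is not a subset of the denominator and the result is not a proportion.

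The design leaves room for such exits. There is one injection per subject (SAP 3.3). Before it come screening, an MRI visit (SAP 4.2), a suitability check and, for women of childbearing potential, a pregnancy test (SAP 4.3). The PET visit may take place up to 3 months after the final A05 visit, which is when screening should occur (SAP 4.1 and 4.3). After the injection little time remains, because the end of "study participation is defined as 48 hours after flortaucipir administration". Most of the opportunity to leave therefore comes before the injection.

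What is at stake is the reported completion and discontinuation rate. The baseline, efficacy and safety tables are confined to injected subjects (SAP 9, 7.1.3 and 15), so the disposition table is where the loss between consent and scan should be visible.

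**Working it through.** **Plan's own figure.** None. The documents state no dropout, completion or discontinuation rate, so the counts below are assumptions and are shown over a range.

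**Notation.**
- E = enrolled (SAP 7.1.1). SAP 3.4 and Protocol 8.1.1 plan about 100; the protocol synopsis says approximately 160.
- a = enrolled subjects who leave before injection (assumed).
- b = subjects who leave after injection (assumed).
- S = E − a = safety population (SAP 7.1.2).
- Completed = S − b. Every enrolled subject is taken to be either completed or discontinued.

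**Formulas.**
1. SAP denominator, all discontinuations counted: discontinued (a + b)/S, completed (S − b)/S. The sum is (a + S)/S = E/S, which exceeds 1 whenever a ≥ 1.
2. SAP denominator, injected subjects only: discontinued b/S, completed (S − b)/S. The sum is 1, but a does not appear in the discontinued rate.
3. Enrolled denominator: discontinued (a + b)/E, completed (S − b)/E. The sum is 1, and a is included.

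**Results for E = 100, b = 1.** Sums are taken from unrounded values.

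| a | S | (1) disc. + compl. = sum | (2) disc. / compl. | (3) disc. / compl. |
|---|---|---|---|---|
| 0 | 100 | 1.0% + 99.0% = 100% | 1.0% / 99.0% | 1.0% / 99.0% |
| 5 | 95 | 6/95 = 6.3% + 94/95 = 98.9% = 105.3% | 1.1% / 98.9% | 6.0% / 94.0% |
| 10 | 90 | 11/90 = 12.2% + 89/90 = 98.9% = 111.1% | 1.1% / 98.9% | 11.0% / 89.0% |
| 20 | 80 | 21/80 = 26.25% + 79/80 = 98.75% = 125.0% | 1.25% / 98.75% | 21.0% / 79.0% |

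Under (1) and (2) the completed percentage stays near 99% however many subjects leave before injection. Under (3) it falls from 99.0% to 79.0%.

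**At the larger planned size.** With E = 160, a = 16 and b = 2, S = 144. Reading (1) gives 18/144 = 12.5% plus 142/144 = 98.6%, a sum of 160/144 = 111.1%.

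**Is a ≥ 1 likely?** If each subject independently has probability p of leaving before injection, the chance of at least one such exit is 1 − (1 − p)^E. For assumed p of 1%, 2% and 5% this is 63%, 87% and 99% with E = 100, and 80%, 96% and nearly 100% with E = 160.

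**The case against.** Several points count against the concern.

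- **It may never arise.** The plan intends that "All subjects who qualify for the study and sign informed consent will receive a single IV bolus of flortaucipir". If no enrolled subject leaves before injection, the two populations coincide and nothing changes. This stands: a reader might infer that the rates are bound to be wrong, but the documents support only the conditional statement.
- **The injected base is legitimate.** Restricted to injected subjects, the percentages sum to 100% and correctly describe completion among those dosed. That also stands, though it answers a narrower question. SAP 8 does not state the restriction, and Protocol 8.3 covers all who discontinue.
- **Attrition is not hidden.** The table prints the enrolled, safety, completed and discontinued counts, so enrolled minus safety gives the pre-injection loss. The listing adds consent date, end date and reason. This stands and limits the harm. It does not make the printed percentage right.
- **Not all exits precede injection.** A reader might infer that almost every discontinuation falls before dosing. The schedule shows only that most of the opportunity does. Technical problems can occur at the scan, about 80 minutes after the dose, and contact can be lost at the follow-up call. A subject found pregnant or unsuitable before injection might also be regarded as failing eligibility (Protocol 5.3.2) and so never entering the Enrolled Population.
- **Other selection comes earlier.** A reader might take loss between consent and scan to be the main selection step. Nothing in the documents shows this. Completing A05 and agreeing to take part also select subjects, and no denominator in this table would reveal that.

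**Conclusion.** The concern holds in conditional form. As written, SAP 8 divides a count not limited to injected subjects by a population that is, and nothing elsewhere in the SAP or protocol corrects it. Once one enrolled subject leaves before injection, the two percentages sum to E/S. The illustrated range of 100% to 125.0% rests on assumed exits of 0 to 20 per 100 enrolled before injection and one after, so it shows how the rule behaves and does not forecast this study.

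Severity is low. One descriptive table is affected, and a reader can recompute the rates from its counts and the listing. The ANCOVA in SAP 14.2 and the safety summaries in SAP 15 do not use these percentages, and the safety population remains the proper base for adverse events.

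**What to change.** In SAP section 8:

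1. Base the Completed and Discontinued percentages on the Enrolled Population of SAP 7.1.1.
2. Show screen failures in a separate row outside that denominator. The table is meant to represent everyone screened, and counting screen failures as discontinued could again push the total above 100%.
3. Split the discontinued count into exits before and after injection, and state that both are included.
4. Keep the number of discontinued subjects as the denominator for reasons.

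The cost is a changed sentence, a few added rows and a new denominator in one table. No new data are needed: consent date, end-of-study date and injection date are already planned for listing (SAP 8 and 15.1). Completion among injected subjects can still be derived from the post-injection row and the safety count.

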9. BASELINE ANALYSIS

All baseline data will be summarized by diagnosis groups for the Safety Analysis Population.

9.1. Baseline Characteristics and Demographics

All baseline data will be gathered from the AV-1451-A05 datasets for confirmatory cohort subjects who participated in AV-1451-A18.

The following data will be reported in the baseline characteristics and demographics table by diagnosis groups using descriptive statistics, and presented in a listing:

- Age (years)
- Gender
- Race
 - Sub-race (if Asian): Japanese; Other
- Ethnicity
- Highest Level of Education
- Alcohol History
- Smoking History
- Recreational Drug History
- MMSE
- Clinical Dementia Rating-Sum of Boxes (CDR-SB)
- Flortaucipir SUVr (MUBADA)
- Tau status according to visual interpretation (majority reading results from 5 independent readers)
- Florbetapir SUVr

9.1.1. Missing Baseline Data

No imputation will be performed on missing baseline demographic data.

9.2. Electrocardiogram

ECG data will be presented in a listing including the following information

- Was an ECG Collected at Screening? (Yes/No); Explanation, if No
- Collection Date/time

9.3. Safety Labs

Safety Lab data will be presented in a listing including the following information

- Were Clinical Labs Collected? (Yes/No); Explanation, if No
- Collection Date

10. MRI DATA ANALYSIS

MRI volumes will be normalized to the intracranial volume, and summarized in a table by diagnosis groups at each visit and CFB using descriptive statistics for the following brain regions.

- Total Brain Volume (excluding ventricle)
- Left Hippocampal Volume
- Right Hippocampal Volume
- Ventricle Volume

The MRI volumes will be presented in a listing with the following.

- Was MRI Performed? (Yes/No)
- Date of Screening MRI
- Was SWI MRI Sequence Collected? (Yes/No)

11. MEDICAL AND SURGICAL HISTORY

Medical and Surgical History will be coded using MedDRA Version 20.0. Medical and surgical history will be presented in a listing including:

- Subject has Medical/Surgical History? (Yes/No)
- System Organ Class (SOC)
- Condition/Disease
- Start Date
- End Date
- Condition Still Present (Yes/No)

12. CONCOMITANT MEDICATION

Medications will be coded using the WHO-Drug Classic December 2016 dictionary.

Concomitant medications are medications that started prior to, on or after the informed consent date *and* ended on or after the date of the flortaucipir injection or were ongoing at the end of the study. This will include any medication continuing from the AV-1451-A05 study.

Medications will be presented in a listing including:

- Medication Name/ Preferred term
- Indication
- Dose
- Dose unit
- Frequency
- Route
- Start date
- End date
- Ongoing (Yes/No)
- Used for Adverse Event? (AE)

12.1.1. Missing and Partially Missing Start and Stop Dates

See appendix 1.1 for specific algorithms to impute missing start and stop dates.

13. FLORTAUCIPIR IMAGING DATA

All flortaucipir imaging data will be summarized by diagnosis groups for the Safety Analysis Population.

13.1. Pregnancy Test

Pregnancy testing information will be presented in a listing including:

- Was a Pregnancy Test Performed? (Yes/No/ N/A)
- Date of Collections
- Result

13.2. PET Scan

The PET scan data will be presented in a listing including:

- Date of PET Imaging
- Scan Emission Start/Stop Time
- Were There Any Deviations From the Standard PET Imaging Protocol? (Yes/No); Explanation, if Yes
- Did the Subject Complete the Protocol-required Imaging Session? (Yes/No); Explanation, if No

14. EFFICACY ANALYSIS

All efficacy analysis will be conducted using the Efficacy Analysis Population.

14.1. Efficacy Variable

Flortaucipir uptake CFB as measured by MUBADA SUVr will be the primary variable of interest. MUBADA CFB will be calculated as the difference between SUVr values from AV-1451-A05 Baseline to the Flortaucipir Imaging Visit under the AV-1451-A18 protocol.

MUBADA and all sub-regional SUVr will be presented in a listing.

14.2. Primary Analysis

14.2.1. Longitudinal Analysis

The flortaucipir image data will be analyzed longitudinally for MUBADA SUVr.

The difference in MUBADA SUVr CFB between diagnosis groups will be tested using the following hypothesis:

$$H_0 : LSM\Delta_{AD} = LSM\Delta_{MCI}$$

$$H_A : LSM\Delta_{AD} \neq LSM\Delta_{MCI}$$

The difference in MUBADA SUVr CFB between Amyloid statuses will be tested using the following hypothesis:

$$H_0 : LSM\Delta_{A\beta+} = LSM\Delta_{A\beta-}$$

$$H_A : LSM\Delta_{A\beta+} \neq LSM\Delta_{A\beta-}$$

where $LSM\Delta^*$ is the respective diagnosis or Amyloid group's LS mean change at the follow-up flortaucipir imaging visit.

An analysis of covariance (ANCOVA) model adjusted for baseline SUVr and age, including the interaction term of diagnosis group and Amyloid status. The appropriate contrasts will be set up to test both longitudinal hypotheses as well as look at the differences between amyloid statuses within each diagnosis group.

A separate table summarizing MUBADA SUVr, and the MUBADA SUVr CFB will be created for each hypothesis, including:

- Descriptive statistics by each group
- LS Mean Changes (SE) by group
- Differences between LS Mean Changes (SE) from contrasts
- 95% Confidence Interval around differences between LS Mean Changes
- P-value from respective contrast

14.2.2. Correlation Analysis

A correlation analysis will be performed to investigate the relationship between MUBADA SUVr CFB and cognitive function CFB as measured by MMSE and CDR-SB. Partial's correlation coefficient (ρ) adjusted for age, baseline MUBADA SUVr, and baseline cognitive score will be calculated to assess the association between changes in cognitive function and tau uptake.

Scatter plots will be generated for MMSE change and SUVr change by Amyloid Beta status. Each plot will include:

- Regression line with ρ
- p-value testing the hypothesis $\rho = 0$

14.2.3. Statistical Considerations in Primary Analysis

All hypothesis testing will be run at a two-sided 0.05 level of significance. No correction for multiplicity will be applied to control for alpha.

ANCOVA models will be run separately for each amyloid status if the assumption of independent identically distributed normal variance is not met by a practical margin. Variances between groups separated by a factor of at least 2 will facilitate the need to run separate models.

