8.2. Efficacy Analysis

The tau deposition measured as AV1451 SUVR values change from baseline (CFB) will be summarized by enrolling clinical diagnosis and amyloid status.

Analysis of covariance (ANCOVA) adjusting for baseline AV1451 SUVR and age will be applied to compare the least square (LS) mean SUVR CFB by clinical diagnosis groups, amyloid status and the interaction of two, through proper contrasts set up. The relationship between SUVR CFB and cognitive function assessments CFB will also be explored with ANCOVA models. The analysis details will be provided in statistical analysis plan (SAP).

Clinical and imaging data from the ¹⁸F-AV-1451-A05 study will be made available to the ¹⁸F-AV-1451-A18 study for these analyses once the database lock and unblinding has occurred for ¹⁸F-AV-1451-A05 study.

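### If the SAP's variance rule sends the primary analysis to separate ANCOVAs by amyloid status and these replace the joint model, the planned Aβ+ versus Aβ- test has no stated method

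*SAP*

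**What the plan says.** SAP 14.2.1 states two hypotheses for the change in MUBADA SUVr: AD versus MCI, and the amyloid comparison ("The difference in MUBADA SUVr CFB between Amyloid statuses will be tested using the following hypothesis"). Both come from a single ANCOVA with baseline SUVr, age and the diagnosis-by-amyloid interaction, in which "contrasts will be set up to test both longitudinal hypotheses as well as look at the differences between amyloid statuses within each diagnosis group". The table for each hypothesis is to show "Differences between LS Mean Changes (SE) from contrasts", a 95% confidence interval and the p-value of the contrast.

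Protocol 8.2 plans the same comparisons of LS means, by "clinical diagnosis groups, amyloid status and the interaction of two, through proper contrasts set up", and leaves the detail to the SAP. SAP section 5 lists only the move to MUBADA as a change from the protocol, so these contrasts are still planned.

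SAP 14.2.3 adds the fallback: "ANCOVA models will be run separately for each amyloid status if the assumption of independent identically distributed normal variance is not met", with the qualifier that the assumption "is not met by a practical margin". The threshold follows: "Variances between groups separated by a factor of at least 2 will facilitate the need to run separate models". The section says nothing more about the separate models.

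**The concern.** A model fitted to one amyloid stratum has no amyloid term. The fallback therefore removes from each fit the factor that one of the two named hypotheses is about, and it does so exactly when the SAP's own trigger is met. The SAP does not say whether the separate fits replace the joint ANCOVA or sit beside it, how Aβ+ and Aβ- are then compared, at what covariate values, with what degrees of freedom, or how two AD versus MCI contrasts become one answer. Those choices would be made after the data had been seen, and they can change the result.

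**Working it through.** **1. What each model can estimate.** Write the joint model of SAP 14.2.1 as

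change = μ(diagnosis, amyloid) + β₁·baseline SUVr + β₂·age + error,

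with four cell means: M+ and A+ (MCI and AD, Aβ+), M- and A- (MCI and AD, Aβ-).

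| Planned contrast | Formula | Joint ANCOVA | Aβ+ fit alone | Aβ- fit alone |
|---|---|---|---|---|
| AD vs MCI | ½(A+ + A-) - ½(M+ + M-) | yes | only A+ - M+ | only A- - M- |
| Aβ+ vs Aβ- | ½(M+ + A+) - ½(M- + A-) | yes | no | no |
| Amyloid within MCI | M+ - M- | yes | no | no |
| Amyloid within AD | A+ - A- | yes | no | no |
| Interaction | (A+ - M+) - (A- - M-) | yes | no | no |

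This part needs no data and no assumption.

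**2. How often the rule would fire.** The plan gives no figure for this, so there is none to reproduce. Inputs: about 60 Aβ+ subjects (SAP 3.4); about 40 Aβ-, derived as 100 - 60; trigger at a ratio of 2 in either direction (SAP 14.2.3); true variance ratio R (Aβ+ over Aβ-) assumed, because no Aβ- SD is given. For normal data,

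P(fire) = P(F ≥ 2/R) + P(F ≤ 0.5/R), with F on (59, 39) df.

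- R = 1: 0.0117 + 0.0079 = 0.020
- R = 1.5: 0.1711 + 0.0001 = 0.171
- R = 2: 0.508
- R = 4: 0.992

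If Aβ- is the more variable group, the figures at ratios 1.5, 2 and 4 are 0.157, 0.492 and 0.988. Using residual variances, with four parameters per fit and so (56, 36) df, gives 0.024, 0.181, 0.509 and 0.990 for Aβ+ larger. The protocol synopsis plans about 160 subjects. At the same 60% positivity that is 96 and 64, and the figures are 0.003, 0.112, 0.506 and 0.999.

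**3. Replacement reading: does the unstated comparison matter?** The two fits use different subjects, so a difference of LS means with SE = √(SE₊² + SE₋²) can be formed. Its value depends on where the LS means are taken. At each fit's own covariate means, the difference is shifted by slope × baseline gap. With an assumed gap of 0.3 and a slope of 0.1 the shift is 0.1 × 0.3 = 0.03. In a simulation of 5,000 runs (60/40, SDs 0.194 and 0.10, no true adjusted amyloid effect), that choice rejected in 5%, 18%, 51% and 83% of runs at slopes 0, 0.1, 0.2 and 0.3. LS means at common covariate values rejected in about 5% throughout. The gap and slopes are hypothetical, and the shift is zero if either is zero.

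**4. Supplementary reading: what the joint model then gives.** For a simple difference of means, ignoring covariates and diagnosis, compare the pooled variance with the true one, setting the smaller variance to 1.

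- Ratio 2, Aβ+ larger: true 2/60 + 1/40 = 0.0583. Pooled [(59×2 + 39×1)/98] × (1/60 + 1/40) = 0.0668. SE ratio √(0.0668/0.0583) = 1.07.
- Ratio 2, Aβ- larger: true 1/60 + 2/40 = 0.0667. Pooled [(59×1 + 39×2)/98] × (1/60 + 1/40) = 0.0582. SE ratio 0.93.

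So at the trigger value itself the pooled standard error is about 7% too large or about 7% too small, depending on which group is more variable.

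**The case against.** The strongest reply is that nothing need be lost. SAP 14.2.3 does not withdraw the contrasts of 14.2.1, the separate fits might be extra, and a statistician can subtract two independent LS means with a proper standard error. That stands against the reading a reader might infer, that the SAP drops the amyloid hypothesis or makes it untestable. The documents do not say so: the test is unspecified, not impossible. What remains is that the choice between replacing and supplementing is not stated, and neither branch has a stated remedy for the amyloid contrast.

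A reader might also infer that the rule would often fire by chance because SAP 14.2.3 does not define the groups, and the four diagnosis-by-amyloid cells would give many more opportunities. The text does not support resting anything on that. Its first sentence names amyloid status, which points to two groups, and its appeal to the ANCOVA assumption points to residual variances. With two groups and equal variances the rule fires about 2% of the time.

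Finally, the stakes are bounded. The sole objective is longitudinal change, the sample size rests on the Aβ+ mean change, and this is an open-label phase 2 study without multiplicity control. That is right, and it limits the damage to the group comparisons.

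**Conclusion.** The gap is real, in conditional form. If the separate models replace the joint one, neither fit can estimate the Aβ+ versus Aβ- contrast, the interaction or the within-diagnosis amyloid differences; AD versus MCI becomes two stratum-specific contrasts; and no rule compares or combines the fits. If they supplement it, the amyloid contrast rests on an equal-variance assumption that the SAP has just declared failed. LS mean changes within each amyloid group and the stratum-specific AD versus MCI contrasts survive either way.

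The structural part is certain. How likely it is to matter is not: the firing rates rest on assumed variance ratios and normal data, and they run from about 2% to 99% at N = 100. The SAP should be corrected before the SUVr changes are analysed, but the gap does not threaten the description of change over time.

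**What to change.** Replace the separate-model rule in SAP 14.2.3 with one pre-specified ANCOVA on all subjects, with residual variances by diagnosis-by-amyloid cell (for example PROC MIXED, REPEATED / GROUP=, with Satterthwaite or Kenward-Roger df). Take every 14.2.1 contrast from it at common baseline SUVr and age, and keep the per-amyloid ANCOVAs as supportive.

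Variances by cell are preferable to variances by amyloid status alone. In simulations at N = 100 with assumed cell sizes and an AD/MCI variance ratio of 2, amyloid-only variances gave type I error of 1.4-1.9% or 8.7-9.1% for the within-diagnosis amyloid contrasts. Cell variances gave 4.3-5.5% for all contrasts.

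The cost is SAP wording and a few lines of SAS, plus two statistical downsides:

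- **Degrees of freedom.** The pooled model has 100 - 6 = 94. With cell variances the simulated average was 64-78 for the overall and interaction contrasts and 29-47 within diagnosis. At 29 df the 95% multiplier is 2.05 instead of 1.99.
- **Common slopes.** The single model keeps 14.2.1's common baseline and age slopes, which separate fits would relax. The supportive per-amyloid fits would show whether this matters.

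If the sponsor keeps the trigger, the minimum change is to state that it uses the residual variances of the two amyloid groups, and that Aβ+ and Aβ- LS means from the two fits are then compared at common covariate values with a Welch/Satterthwaite test. In simulation at a variance ratio of 2.5 that comparison held its error at 4.3-5.8%.

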3.4. Sample Size Justification

This study is estimated to enroll about 100 subjects from A05 confirmatory arm. Current analyses with A05 exploratory arm data showed that for subjects met A05 confirmatory arm enrollment criteria (MCI or demented, Mini Mental State Exam (MMSE) between 20 and 27), flortaucipir SUVR on average changed 0.0527 (SD=0.0970) for amyloid positive subjects at 9 months follow up. Assume a similar amyloid positivity to A05 exploratory arm (~60%), and assume the change of flortaucipir SUVR is linear, this study is expected to have approximately 60 amyloid positive subjects and the mean change of flortaucipir SUVR is expected to be 0.105, with a 95% confidence interval (0.0635, 0.1473).

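### The SAP's only remedy for unequal variances is to split by amyloid status, so the primary AD vs MCI contrast has no protection if AD and MCI variances differ

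*SAP*

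**What the plan says.** SAP 14.2.1 sets two primary hypotheses on change in MUBADA SUVr. One is amyloid positive vs negative. The other is diagnosis: "The difference in MUBADA SUVr CFB between diagnosis groups will be tested using the following hypothesis". Both come from one model: "An analysis of covariance (ANCOVA) model adjusted for baseline SUVr and age, including the interaction term of diagnosis group and Amyloid status". No unequal-variance option is given, so I read this as the usual single residual variance over the four diagnosis-by-amyloid cells. The tables report "Differences between LS Mean Changes (SE) from contrasts", with 95% confidence intervals and p-values.

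SAP 14.2.3 then allows for the variance assumption to fail: "ANCOVA models will be run separately for each amyloid status if the assumption of independent identically distributed normal variance is not met", to which it adds that the failure must be by a practical margin. The threshold follows: "Variances between groups separated by a factor of at least 2 will facilitate the need to run separate models". The same section fixes the level: "All hypothesis testing will be run at a two-sided 0.05 level of significance". It also states: "No correction for multiplicity will be applied to control for alpha".

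**The concern.** The rule's remedy and one of the two primary tests do not line up. Splitting by amyloid status allows Aβ+ and Aβ- subjects to have different residual variances. It does nothing for AD and MCI, which are still pooled inside each amyloid model. Neither document offers group-specific variances, a Welch-type test, robust standard errors or a split by diagnosis.

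The undefined word *groups* does not rescue the plan. If it covers diagnosis groups or the four cells, the trigger can fire for a cause that the remedy does not treat. If it means only the two amyloid groups, unequal AD and MCI variances trigger nothing. On both readings the AD vs MCI standard error is left alone.

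At stake are the standard error, confidence interval and p-value of a primary contrast. With unequal group sizes a pooled variance makes them too small when the smaller group is the more variable, and too large in the opposite case. A second issue is that the model is chosen by comparing sample variances, so the analysis reported depends partly on chance.

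**Working it through.** **Inputs from the documents.** Two-sided level 0.05 (SAP 14.2.3). N about 100: "This study is estimated to enroll about 100 subjects from A05 confirmatory arm" (SAP 3.4). The protocol synopsis gives about 160. About 60% amyloid positive, hence about 60/40 (SAP 3.4).

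**Inputs that are not in the documents, so assumed.** AD share of 20% to 80%. AD:MCI variance ratio of 2 to 4. Cell layouts as stated below. The only SD given is 0.0970, for amyloid-positive subjects at 9 months. There is none by diagnosis.

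**Step 1. Reproduce the plan's figure.** With equal variances, simulation of the SAP's ANCOVA (two covariates, 20,000 trials per setting) gives a level of 4.8-5.3% for AD vs MCI. The stated 0.05 is reproduced.

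**Step 2. Large-sample formula.** For group sizes n1, n2 and variances v1, v2:

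- true variance of the difference: V = v1/n1 + v2/n2
- variance the pooled model reports on average: P = s² × (1/n1 + 1/n2), with s² = [(n1-1)v1 + (n2-1)v2] / (n1+n2-2)
- actual level: 2 × [1 - Φ(1.96/√(V/P))]

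With AD variance 2 and MCI variance 1:

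- AD 30, MCI 70: V = 2/30 + 1/70 = 0.0810. s² = (29×2 + 69)/98 = 1.296. P = 1.296 × 0.0476 = 0.0617. V/P = 1.312, level 8.7%.
- AD 50, MCI 50: V = 0.06, P = 1.5 × 0.04 = 0.06. V/P = 1, level 5.0%.
- AD 70, MCI 30: V = 0.0619. s² = (69×2 + 29)/98 = 1.704. P = 0.0811. V/P = 0.763, level 2.5%.

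**Step 3. Full ANCOVA by simulation**, joint model, N = 100, AD the more variable group. Level of the AD vs MCI test:

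| AD share | ratio 2 | ratio 3 | ratio 4 |
|---|---|---|---|
| 20% | 11.2% | 15.4% | 18.1% |
| 30% | 8.7% | 10.9% | 12.6% |
| 40% | 6.8% | 7.5% | 8.5% |
| 50% | 5.1% | 5.1% | 5.2% |
| 60% | 3.6% | 3.1% | 3.0% |
| 70% | 2.5% | 1.8% | 1.4% |
| 80% | 1.8% | 0.9% | 0.6% |

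N = 160 gives nearly the same values.

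**Step 4. Apply the SAP's split.** With a 30% AD share in both amyloid strata, the level at ratios 2, 3 and 4 is 8.7, 10.8 and 12.5% within Aβ+ and 8.3, 10.6 and 12.5% within Aβ-. The split repairs nothing.

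If AD subjects are more often amyloid positive, the strata diverge. Take assumed cells AD+/AD-/MCI+/MCI- of 30/10/30/30:

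- AD variance 2 and 3 times MCI: joint test about 7.1% and 8.5%, Aβ+ model about 5% at both, Aβ- model (10 vs 30) about 9.6% and 12.8%.
- MCI the more variable, ratios 2 and 3: joint test about 3.2% and 2.5%, Aβ- model about 2.1% and 1.3%.
- A test with cell-specific variances and Satterthwaite-type degrees of freedom (checked without covariates): 4.8-5.2% in all these settings, including the cell of 10.

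**Step 5. How often the rule fires.** If *groups* means the amyloid groups at 60/40, the ratio of sample variances is the true ratio times an F(59, 39) variable (ignoring the degrees of freedom used by the model). The probability that it is at least 2 or at most 1/2, with Aβ+ the more variable, is 2.0% at a true ratio of 1, 17% at 1.5 and 44% at 1.9. If *groups* means the four cells, taken as 30/10/30/30, the largest-to-smallest ratio reaches 2 in 43% of trials even when all variances are equal.

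**The case against.** The strongest reply is that the trigger sentence directly follows the one on amyloid status, so *groups* most naturally means the two amyloid groups, and trigger and remedy then match. That is a fair reading. It removes the claim that the rule is set off by any groups at all, but the gap for AD vs MCI remains.

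Three stronger statements are tempting, and the documents do not support them.

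- A reader might infer that the AD vs MCI test runs at 7-13%. That needs the smaller group to be the more variable one, and nothing in either document says so. Step 3 shows that the same plan can give 5% or well under.
- A reader might infer that the rule fires by chance in 43% of trials. That holds only for the four-cell reading with an assumed cell of 10. For the 60/40 amyloid groups with equal variances the figure is 2% (0.3% at 96/64, for N = 160).
- A reader might infer that pooled standard errors always stay in force when the true amyloid ratio is below 2. The trigger uses sample variances, and at a true ratio of 1.9 the split is made in about 44% of trials. The fault there is an unstable choice of model, not one fixed error rate.

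It can also be said that this is an open-label phase 2 study with a descriptive objective, that tests are openly unadjusted for multiplicity, and that the documents tie no decision to the AD vs MCI p-value. That limits the consequences. It does not make the reported intervals correct.

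**Conclusion.** The concern holds in conditional form. The structural part follows from the text alone: the SAP foresees unequal variances, leaves *groups* undefined, and gives a remedy that cannot reach the AD vs MCI contrast.

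The size depends on an AD:MCI split and a variance ratio that the documents do not give. The level is about 7-13% if the more variable group is 30-40% of subjects with a ratio of 2-4, about 5% at 50:50, and below 5% with lost power if the larger group is the more variable. With AD the more variable group, an AD share of 20-80% and ratios of 2-4 give about 0.5% to 18%. Because the direction cannot be known in advance, a method that is valid either way is preferable. This is a worthwhile and cheap correction, not a flaw that undermines the study.

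**What to change.** In SAP 14.2.3, delete the factor-of-2 rule and the split by amyloid status. In SAP 14.2.1, pre-specify without conditions:

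- one ANCOVA with diagnosis, amyloid status, their interaction, baseline SUVr and age;
- a separate residual variance for each of the four diagnosis-by-amyloid cells (PROC MIXED with REPEATED / GROUP=);
- Satterthwaite or Kenward-Roger degrees of freedom, with one of the two named in the SAP;
- every contrast, standard error, confidence interval and p-value taken from this model.

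Do not add a fallback to robust (HC3) standard errors for small cells. Without a threshold fixed in advance it would be another data-dependent switch, and the check with a cell of 10 held its level without it.

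The cost is a few lines of SAP text, one SAS statement, and a few degrees of freedom if the variances turn out equal.
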